11.7.6 Achenbach CBCL

The Achenbach CBCL is a widely used validated questionnaire to evaluate a child's competencies and behavioral/emotional problems. Behavioral problems will be scored by the parent(s)/legal representative(s)/caregiver(s). The CBCL/1½-5 checklist for children 18 months to 5 years and 11 months of age will be used in this study. The Achenbach CBCL/1½-5 will be completed by the parent(s)/legal representative(s)/caregiver(s) of subjects \geq 18 months of age at Visit 3. The Achenbach CBCL will be administered only in countries where a translated version is available.

The scale will be completed in accordance with the tabular schedules of study procedures (Section 5.2) and should be completed by the same parent(s)/legal representative(s)/caregiver(s). The completion of the Achenbach CBCL will require approximately 45 minutes.

In the CBCL/1½-5 checklist, the occurrence of certain problems and behaviors at the time of administering the questionnaire or within the past 2 months will be scored on the following scale:

- 0=not true (as far as known)
- 1=somewhat or sometimes true
- 2=very true or often true

Eight syndrome scores will be calculated from these questions, which will in turn be summarized by 2 composite scores. Additionally, for each score on the question, syndrome, and total level,

categorizations based on a normative sample will be used to evaluate normal, borderline, or clinically relevant behavior.

Baseline assessment of the Achenbach CBCL will be performed at Visit 3; however, due to the short study duration of SP0967, the next assessment will be collected in subjects entering into the EP0034 study. Thus, the analysis of these data will be conducted in EP0034.

11.7.7 BRIEF-P

The BRIEF-P is a validated tool that will be used for the evaluation of subjects ≥ 2 years of age and will be administered according to the tabular schedules of study procedures (Section 5.2). The BRIEF-P will be administered only in countries where a translated version is available.

The BRIEF-P includes rating forms used by parents to assess subjects' executive functioning within the context of the subject's everyday environment. It requires that the parent must have had recent and extensive contact with the child over the past 6 months. Executive functions broadly encompass a set of cognitive skills that are responsible for the planning, initiation, sequencing, and monitoring of complex goal directed behavior.

The BRIEF-P rating form consists of items that measure various aspects of executive functioning: Inhibit, Shift, Emotional Control, Working Memory, and Plan/Organize. The clinical scales form 3 broad overlapping indexes: Inhibitory Self-Control (Inhibit and Emotional Control), Flexibility (Shift and Emotional Control), and Emergent Metacognition (Working Memory and Plan/Organize) and 1 composite score (Global Executive Composite).

The BRIEF-P includes validity scales to measure negativity and inconsistency of responses.

Baseline assessment of the BRIEF-P will be performed at Visit 3; however, due to the short study duration of SP0967, the next assessment will be collected in subjects entering into the EP0034 study. Thus, the analysis of these data will be conducted in EP0034.

11.7.8 Bayley Scales of Infant and Toddler Development, Third Edition

The Bayley-III scales are recognized internationally as one of the most comprehensive developmental assessment instruments (Sattler and Hoge, 2006) used to examine the major facets of a young child's development (Bayley, 2006). The Bayley-III scales are a standardized, individually administered, adaptive assessment that measures the developmental functioning of infants and young pediatric subjects from 1 month to 42 months of age (Bayley, 2006). The Bayley-III scales measure cognitive, language, motor, social-emotional, and adaptive development and are a revision of the predecessor, the Bayley Scales of Infant Development, Second Edition (Bayley, 1993). The Bayley-III scales are a technically sound instrument, with strong internal consistency, as well as test-retest stability. The Bayley-III scales are validated only in English.

The scales are validated as a tool for assessment of neurological development in young pediatric subjects and are therefore considered appropriate for SP0967.

The Bayley-III scales are an individually administered, adaptive assessment that presents pediatric subjects with situations and tasks designed to produce an observable set of behavioral responses. They consist of a cognitive scale, a language composite scale with receptive and expressive language subscales, and a motor composite scale with fine and gross motor subscales

to be completed by the investigator or designee. It also has a social emotional scale, comprising social-emotional competence, and sensory processing, and an adaptive behavior scale, which assesses the attainment of skills necessary for the development of independence, to be completed by the child's parent(s)/legal representative(s)/caregiver(s).

The completion of the Bayley-III scales will require approximately 50 minutes for pediatric subjects who are 12 months old or younger and 90 minutes for pediatric subjects aged 12 months to 18 months.

Investigators must make every attempt to administer the scale according to the tabular schedules of study procedures (Section 5.2). If needed, the investigators may utilize trained pediatric psychologists or other appropriately skilled individuals to administer the scale.

Due to the short study duration of SP0967, the next assessment will be collected in subjects entering into the EP0034 study. Thus, the analysis of these data will be conducted in EP0034.

12 STUDY MANAGEMENT AND ADMINISTRATION

12.1 Adherence to protocol

The investigator should not deviate from the protocol. However, the investigator should take any measure necessary in deviation from or not defined by the protocol in order to protect clinical study subjects from any immediate hazard to their health and safety. In this case, this action should be taken immediately, without prior notification of the regulatory authority, IRB/IEC, or sponsor. After implementation of such measure, the investigator must notify the Clinical Project Manager (CPM) of the sponsor within 24 hours and follow any local regulatory requirements.

12.2 Monitoring

UCB (or designee) will monitor the study to meet the sponsor's monitoring Standard Operating Procedures (SOPs), ICH-GCP guideline, and applicable regulatory requirements, and to ensure that study initiation, conduct, and closure are adequate. Monitoring of the study may be delegated by UCB to a contract research organization (CRO) or a contract monitor.

The investigator and his/her staff are expected to cooperate with UCB (or designee) and to be available during the monitoring visits to answer questions sufficiently and to provide any missing information. The investigator(s)/institution(s) will permit direct access to source data/documents for study-related monitoring, audits, IRB/IEC review, and regulatory inspection(s).

The investigator will allow UCB (or designee) to periodically review all eCRFs and corresponding source documents (eg, hospital and laboratory records for each study participant). Monitoring visits will provide UCB (or designee) with the opportunity to evaluate the progress of the study, verify the accuracy and completeness of eCRFs, ensure that all protocol requirements, applicable authority(ies) regulations, and investigator's obligations are being fulfilled, and resolve any inconsistencies in the study records.

12.2.1 Definition of source data

All source documents must be accurate, clear, unambiguous, permanent, and capable of being audited. They should be made using some permanent form of recording (ink, typing, printing, optical disc). They should not be obscured by correction fluid or have temporary attachments

(such as removable self-stick notes). Photocopies and/or printouts of eCRFs are not considered acceptable source documents.

Source documents are original records in which raw data are first recorded. These may include hospital/clinic/general practitioner records, charts, diaries, x-rays, laboratory results, printouts, pharmacy records, care records, ECG or other printouts, completed scales, or quality of life questionnaires, for example. Source documents should be kept in a secure, limited access area.

Source documents that are computer generated and stored electronically must be printed for review by the monitor (eg, ECG reports). Once printed, these copies should be signed and dated by the investigator and become a permanent part of the subject's source documents. The investigator will facilitate the process for enabling the monitor to compare the content of the printout and the data stored in the computer to ensure all data are consistent.

Electronic data records, such as Holter monitor records or electroencephalogram records, must be saved and stored as instructed by UCB (or designee).

12.2.2 Source data verification

Source data verification ensures accuracy and credibility of the data obtained. During monitoring visits, reported data are reviewed with regard to being accurate, complete, and verifiable from source documents (eg, subject files, recordings from automated instruments, tracings [ECG], x-ray films, laboratory notes). All data reported on the eCRF should be supported by source documents, unless otherwise specified in Section 12.2.1.

12.3 Data handling

12.3.1 Case Report form completion

This study is performed using remote data capture (RDC). The investigator is responsible for prompt reporting of accurate, complete, and legible data in the eCRFs and in all required reports.

Any change or correction to the eCRF after saving must be accompanied by a reason for the change.

Corrections made after the investigator's review and approval (by means of a password/electronic signature) will be reapproved by the investigator.

The investigator should maintain a list of personnel authorized to enter data into the electronic eCRF.

Detailed instructions will be provided in the eCRF Completion Guidelines.

12.3.2 Database entry and reconciliation

Case Report forms/external electronic data will be entered/loaded into a validated electronic database using a clinical data management system (CDMS). Computerized data cleaning checks will be used in addition to manual review to check for discrepancies and to ensure consistency of the data. Case Report form data are entered into the clinical database using independent, double-data entry, with the exception of comment fields, which are verified by a second person. In the event that the study is performed using RDC, the data are entered into the eCRFs once and are subsequently verified.

An electronic audit trail system will be maintained within the CDMS to track all data changes in the database once the data have been saved initially into the system or electronically loaded. Regular backups of the electronic data will be performed.

12.3.3 Subject Screening and Enrollment log/Subject Identification Code list

The subject's screening and enrollment will be recorded in the Subject Screening and Enrollment Log.

The investigator will keep a Subject Identification Code list. This list remains with the investigator and is used for unambiguous identification of each subject.

The subject's consent and enrollment in the study must be recorded in the subject's medical record. These data should identify the study and document the dates of the subject's participation.

12.4 Termination of the study

UCB reserves the right to temporarily suspend or prematurely discontinue this study either at a single site, multiple sites, or at all sites at any time for reasons including, but not limited to, safety or ethical issues, inaccurate or incomplete data recording, noncompliance, or unsatisfactory enrollment with respect to quality or quantity.

If the study is prematurely terminated or suspended, UCB (or its representative) will inform the investigators/institutions and the regulatory authority(ies) of the termination or suspension and the reason(s) for the termination or suspension, in accordance with applicable regulatory requirement(s). The IRB/IEC should also be informed and provided with reason(s) for the termination or suspension by the sponsor or by the investigator/institution, as specified by the applicable regulatory requirement(s). In addition, arrangements will be made for the return of all unused study medication and other material in accordance with UCB procedures for the study.

12.5 Archiving and data retention

The investigator will maintain adequate records for the study, including eCRFs, medical records, laboratory results, Informed Consent documents, drug dispensing and disposition records, safety reports, information regarding participants who discontinued, and other pertinent data.

All essential documents are to be retained by the investigator until at least 2 years after the last approval of a marketing application in an ICH region and until there are no pending or contemplated marketing applications in an ICH region, or at least 2 years have elapsed since the formal discontinuation of clinical development of the investigational product. These documents should be retained for a longer period, however, if required by the applicable regulatory requirement(s) or by an agreement with UCB (Committee for Proprietary Medicinal Products [CPMP]/ICH/135/95, 2002 [Section 4.9.5]). The investigator will contact UCB for authorization prior to the destruction of any study records or in the event of accidental loss or destruction of any study records. The investigator will also notify UCB should he/she relocate or move the study-related files to a location other than that specified in the sponsor's trial master file.

12.6 Audit and inspection

The investigator will permit study-related audits mandated by UCB, after reasonable notice, and inspections by domestic or foreign regulatory authorities.

The main purposes of an audit or inspection are to confirm that the rights and well-being of the subjects enrolled have been protected, that enrolled subjects (ie, signing consent and undergoing study procedures) are appropriate for the study, and that all data relevant for the evaluation of the IMP have been processed and reported in compliance with the planned arrangements, the protocol, investigational site, and IRB/IEC SOPs, ICH GCP, and applicable regulatory requirements.

The investigator will provide direct access to all study documents, source records, and source data. If an inspection by a regulatory authority is announced, the investigator will immediately inform UCB (or designee).

12.7 Good Clinical Practice

Noncompliance with the protocol, ICH-GCP, or local regulatory requirements by the investigator, institution, institution staff, or designees of the sponsor will lead to prompt action by UCB to secure compliance. Continued noncompliance may result in the termination of the site's involvement in the study.

13 STATISTICS

A description of statistical methods is presented below and will be described in more detail in the Statistical Analysis Plan (SAP).

13.1 Definition of analysis sets

The Safety Set (SS) will include all randomized subjects who took at least 1 dose of study medication. This is the primary analysis set for the safety variables.

The primary analysis set for the efficacy data will be the Full Analysis Set (FAS), which will include all subjects in the SS.

The secondary analysis set for the efficacy data will be the Per-Protocol Set (PPS), which includes all subjects in the FAS who did not have important protocol deviations related to efficacy.

The Pharmacokinetic Per-Protocol Set (PK-PPS) will consist of all subjects having provided at least 1 measurable postdose plasma sample (with recorded sampling time) on at least 1 visit with documented study medication intake times.

13.1.1 Analysis of the primary efficacy variable

Analyses of the primary efficacy variables are based on the ADF of electrographic partial-onset seizures.

Partial-onset seizure count will be based on electrographic seizures. Electrographic seizures are defined as recognizable ictal patterns on an EEG involving ≥ 2 contiguous electrodes. The seizures are initiated as a unilateral or strongly asymmetric abnormal epileptiform discharge lasting a total of >10 seconds. The video-EEG recordings will be evaluated for seizure counts locally by the investigator, subinvestigator, or qualified designated reader. Subjects who discontinue on or before Day 20 will not require a video-EEG.

Partial-onset seizure frequency for infants aged ≥ 1 month to ≤ 6 months will be based on electrographic seizures. Partial-onset seizure frequency for children aged >6 months to <4 years will be based on electrographic seizures with an accompanying clinical correlate.

Calculation of the Baseline Period ADF of electrographic partial-onset seizures and the Maintenance Period ADF of electrographic partial-onset seizures will be based on results from a video-EEG (up to 72 hours of continuous recording with every attempt to obtain at least 48 hours of interpretable recording) during each period. Subjects are expected to have at least 48 hours of interpretable video-EEG during each period. For subjects who drop out during the End-of-Maintenance Period video-EEG, the number of hours from the start of the End-of-Maintenance Period video-EEG to the time of withdrawal (in hours) will be considered for analysis.

The ADF of electrographic partial-onset seizures will be calculated as (number of partial-onset seizures recorded on the video-EEG divided by the number of interpretable hours recorded) multiplied by 24.

13.1.1.1 Analysis of the primary efficacy variable for the US

Contingent upon $\leq 10\%$ of subjects discontinuing early from the study, the primary efficacy parameter for the US is the change in ADF of electrographic partial-onset seizures during the Maintenance Period compared to the end of the Baseline Period. Seizure ADF will be analyzed using analysis of covariance with terms for treatment, age category (4 age stratification categories, pooled as appropriate), and center (properly pooled), on log-transformed seizure ADF using the transformation of $\ln(X+1)$, where X is the seizure ADF. Log-transformed Baseline seizure ADF will be used as a covariate. The seizure ADF between LCM and PBO will be compared using least squares means (LSMs). The percent reduction over PBO will be estimated as $100 \times (1 - \exp[\text{LSM Treatment } \{\text{TRT}\} - \text{LSMPBO}])$. The analysis of this efficacy variable will consist of all subjects in the FAS who have at least 48 hours of interpretable recordings during both the End-of-Baseline Period video-EEG and the End-of-Maintenance Period video-EEG.

The following additional sensitivity analyses on this primary efficacy variable will be conducted in order to assess the effect of early discontinuations, protocol deviations, and operational bias on this primary endpoint:

- Repeat the primary analysis using the PPS.
- Repeat the primary analysis using the FAS, except missing ADF of partial-onset seizures from the End-of-Maintenance Period video-EEG will be replaced using the Baseline observation-carried-forward approach. This will be applied for all subjects who discontinued early from the study.
- Repeat the primary analysis using the FAS, except missing ADF of partial-onset seizures from the End-of-Maintenance Period video-EEG will be replaced by the overall mean ADF of partial-onset seizures from the End-of-Maintenance Period video-EEG from the subject's respective treatment arm. This will be applied for all subjects who discontinued early from the study.

- Repeat the primary analysis using the FAS, except missing ADF of partial-onset seizures from the End-of-Maintenance Period video-EEG will be replaced using multiple imputation by treatment arm and age group (≥ 1 month to < 6 months of age, ≥ 6 months to < 1 year of age, ≥ 1 year to < 2 years of age, and ≥ 2 years to < 4 years of age) using monotone regression. This will be applied for all subjects who discontinued early from the study.
- Repeat the primary analysis using the FAS for all subjects who have at least 24 hours of interpretable recordings during both the End-of-Baseline Period video-EEG and the End-of-Maintenance Period video-EEG.

Contingent upon $> 10\%$ of subjects discontinuing early from the study, the primary efficacy parameter for the US is identical to the primary efficacy parameter for the EU, described below. The endpoint not designated as primary will still be summarized as a secondary efficacy parameter.

13.1.1.2 Analysis of the primary efficacy variable for the EU

The primary efficacy parameter for the EU is the proportion of responders during the Maintenance Period. Subjects with a 50% or more reduction in seizure ADF will be categorized as responders; this classification requires at least 48 hours of interpretable recordings during both the End-of-Baseline Period video-EEG and the End-of-Maintenance Period video-EEG. The proportion of responders between LCM and PBO will be analyzed using logistic regression with age category (4 age stratification categories, pooled as appropriate) and center (properly pooled) as factors. Subjects who withdraw or drop out before the first 48 hours of the End-of-Maintenance Period video-EEG with reasons related to lack of efficacy will be considered non responders; all other subjects will be missing for this analysis. The number and percentage of subjects with a 50% or more reduction in seizure ADF will be presented by treatment group.

The following additional sensitivity analyses on this primary efficacy variable will be conducted in order to assess the effect of early discontinuations, protocol deviations, and operational bias on this primary endpoint:

- Repeat the primary analysis using the PPS.
- Repeat the primary analysis using the FAS, except subjects who discontinued from the study prior to performance of the End-of-Maintenance Period video-EEG with reasons related to lack of efficacy will be considered non responders, and subjects who discontinued from the study early for any other reason will be considered responders.
- Repeat the primary analysis using the FAS, except all subjects who discontinued from the study early will be considered non responders.
- Repeat the primary analysis using the FAS, except missing ADF of partial-onset seizures from the End-of-Maintenance Period video-EEG will be replaced using multiple imputation by treatment arm and age group (≥ 1 month to < 6 months of age, ≥ 6 months to < 1 year of age, ≥ 1 year to < 2 years of age, and ≥ 2 years to < 4 years of age) using monotone regression. This will be applied for all subjects who discontinued from the study early, and the imputed End-of-Maintenance Period ADF of partial-onset seizures will be used to determine whether a subject is a responder.

- Repeat the primary analysis using the FAS for all subjects who have at least 24 hours of interpretable recordings during both the end of Baseline Period video-EEG and the end of Maintenance Period video-EEG.

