Contingent upon >10% of subjects discontinuing early from the study, the primary efficacy variable for the US is identical to the primary efficacy variable for the EU, described in Section 8.1.1.2.

Whichever of these efficacy variables are not designated as the primary efficacy variable will still be summarized as a secondary efficacy variable.

Primary analysis of the primary efficacy variable for the EU 8.1.2.2

The primary efficacy variable for the EU is the proportion of responders during the Maintenance Period. Subjects with a 50% or more reduction in seizure ADF will be categorized as responders. This classification requires at least 48 hours of interpretable recordings during both the End-of-Baseline Period video-EEG and the End-of-Maintenance Period video-EEG. Subjects who withdraw or drop out before the first 48 hours of the End-of-Maintenance Period video-EEG with reasons related to lack of efficacy will be considered non-responders and will be included in the analysis; all other subjects will be missing and will not be included in this analysis.

Subjects with 0 seizures at Baseline will be missing their Percent Change from Baseline. Subjects with 0 seizures at Baseline will be considered non-responders.

The proportion of responders between LCM and placebo will be analyzed using logistic regression with treatment, age category (4 age stratification categories, pooled as appropriate) and center (pooled appropriately) as factors. From this model, odds ratios will be presented along with the corresponding 95% CI and p-value. In addition, the number and percentage of subjects with a group. with a 50% or more reduction in seizure ADF will be presented by treatment group and age

Sensitivity analyses of the primary efficacy variables

For sensitivity analyses that are applied to subjects who discontinued early, the population will include all subjects with at least 48 interpretable hours of EEG data at both the End-of-Baseline Period video-EEG and the End-of-Maintenance Period video-EEG, and additionally all subjects

with at least 48 interpretable hours of End-of-Baseline Period video-EEG and missing status for End-of-Maintenance Period video-EEG as a consequence of early discontinuation.

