8.1.3.2 Sensitivity analyses of the primary efficacy variable for the EU

The following additional sensitivity analyses on this primary efficacy variable will be conducted in order to assess the effect of modified data cleaning and reconciliation processes, early discontinuations, protocol deviations, and operational bias on this primary endpoint. All sensitivity analyses require at least 48 hours of interpretable recordings during both the End-of-Baseline Period video-EEG and the End-of-Maintenance Period video-EEG, unless otherwise noted. Sensitivity analyses are as follows:

Repeat the primary analysis for the PPS.

- Repeat the primary analysis for the FAS-SDV.
- Repeat the primary analysis for the FAS, except subjects who discontinued from the study prior to performance of the End-of-Maintenance Period video-EEG with reasons related to lack of efficacy will still be considered non-responders, and subjects who discontinued from the study early for any other reason will be considered instead of missing.

Repeat the primary analysis for the first 244 subjects enrolled in the study for the FAS.

- Repeat the primary analysis for the FAS, except all subjects who discontinued from the study early will be considered non-responders.
- Repeat the primary analysis for the FAS, except missing ADF of partial-onset seizures from the End-of-Maintenance Period video-EEG will be replaced using multiple imputation by treatment group, including age group (≥ 1 month to < 6 months of age, ≥ 6 months to <1 year of age, ≥ 1 year to <2 years of age, and ≥ 2 years to <4 years of age) and other appropriate variables (details provided in Section & 1.3.3) using Monotone regression. This will be applied for all subjects who discontinued from the study early, and the imputed End-of-Maintenance Period ADF of partial-onset seizures will be used to determine whether a subject is a responder.
- Repeat the primary analysis for the FAS for all subjects who have at least 24 hours of interpretable recordings during both the end of Baseline Period video-EEG and the end of Maintenance Period video-EEG (rather than 48 hours). Noting that subjects who withdraw or drop out before the first 24 hours of the End-of-Maintenance Period video-EEG with reasons related to lack of efficacy will be considered non-responders and will be included in the analysis; all other subjects will be missing and will not be included in this analysis.

Multiple imputation 8.1.3.3

Imputation Step

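### Two checks on early discontinuation need changing: the US arm-mean imputation understates its standard error, and the EU multiple imputation drops the lack-of-efficacy rule; the primary analysis stands

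*Protocol*

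**What the plan says.** **Primary responder rule.** Protocol 13.1.1.2 keeps a withdrawal before the first 48 hours of the End-of-Maintenance EEG only if it relates to lack of efficacy, as a non-responder; "all other subjects will be missing for this analysis". SAP 8.1.2.2 agrees: "all other subjects will be missing and will not be included in this analysis".

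**US endpoint.** Under Protocol 4.1.1, change in average daily frequency (ADF) is primary for the US only if at most 10% of subjects discontinue early. Above that, the responder endpoint takes over and the ADF endpoint is summarized as secondary.

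**US checks** (Protocol 13.1.1.1, SAP 8.1.3.1). For subjects who discontinued early, the missing ADF is handled in three ways: baseline carried forward, multiple imputation, and an analysis in which it "will be replaced by the overall mean ADF of partial-onset seizures" in the subject's own arm.

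**EU checks** (Protocol 13.1.1.2, SAP 8.1.3.2).
- Other-reason exits as successes: "subjects who discontinued from the study early for any other reason will be considered responders". The SAP adds that exits "related to lack of efficacy will still be considered non-responders".
- All exits as failures: the primary analysis is repeated, "except all subjects who discontinued from the study early will be considered non responders".
- A 24-hour version, in which exits "before the first 24 hours of the End-of-Maintenance Period video-EEG with reasons related to lack of efficacy will be considered non-responders".
- Multiple imputation: "This will be applied for all subjects who discontinued from the study early". SAP 8.1.3.3 imputes ln(X+1) by arm under missing at random and derives responder status from the imputed value. It makes no exception for lack-of-efficacy exits.

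**The concern.** These checks are the plan's evidence on whether early discontinuation affects the result, so each should have valid error bars and vary one thing at a time.

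The arm-mean check has two faults. A constant carries no sampling variation, yet the model counts each filled-in subject as an independent observation. And an arithmetic mean of skewed counts, once put through ln(X+1), lies above the mean of the logged values, so it pushes up whichever arm has more gaps.

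The EU multiple imputation is a standard method, but it is the only EU check that releases lack-of-efficacy dropouts from non-response. If it differs from the primary, the missing-at-random assumption and the released rule are confounded.

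**Working it through.** Dropout is written placebo/LCM in percent. The documents give no split by arm or reason, so all splits are assumptions.

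**1. The plan's own figures** (Protocol 13.6). Difference -0.249 and SD 0.62 give 99 per arm by two-sample t (power 80.3%). Exact enumeration of the continuity-corrected chi-square at 20% v 40% with 99 per arm gives 83.9% (plan: about 83%). Enrolment: 99 / (0.86 × 0.95) = 121.2, so 122. All reproduce. Below, 122 × 0.95 = 116 per arm.

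**2. US arm-mean imputation, first-order arithmetic.** Let a fraction d be filled with a constant. Residual variance shrinks by about (1 - d), and the model uses n where only n(1 - d) values exist. So model SE / true SE ≈ √(1 - d) × √(1 - d) = 1 - d, and rejection under no effect ≈ 2 × [1 - Φ(1.96(1 - d))].
- d = 5%: 1.96 × 0.95 = 1.862, giving 6.3%.
- d = 10%: 1.96 × 0.90 = 1.764, giving 7.8%.

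**3. US arm-mean imputation, simulation.** No effect; random dropout; 116 per arm; log-normal daily rates (log-mean 0.7 or 1.5, between-subject SD 0.8-1.5, within-subject SD 0.35-0.50); Poisson counts over 60 hours; at least 2 baseline seizures; ANCOVA of ln(X+1) on treatment and baseline; residual SD 0.49-0.64 against the planned 0.62; seven settings, two seeds, 4,000 runs each.

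| Dropout | Two-sided rejection at nominal 5% |
|---|---|
| 0/0 | 4.3-5.4% |
| 5/5 | 5.2-7.0% |
| 8/8 | 6.2-7.7% |
| 10/10 | 7.3-8.9% (model SE 0.063-0.096; true SD 0.072-0.108) |
| 6/10 (8% overall) | 7.3-9.6%: 1.5-3.2% favouring LCM, 4.7-7.7% against |

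A second model (122 per arm, residual SD 0.62) separates the two faults. At 14/14 the raw mean rejects 9-10%; filling in the log-scale mean instead still rejects 9-10%, so the standard-error fault does not depend on scale. At 8/20 the raw mean shifts the estimate by +0.03 to +0.10, against LCM, and the log-scale mean does not. Complete-case and baseline-carried-forward analyses stay at 4-6%.

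**4. EU multiple imputation.** Assume 7% lack-of-efficacy and 7% other exits in each arm, and 20% v 40% response among completers.
- Primary rule: 0.20 × 0.86/0.93 = 18.5% v 0.40 × 0.86/0.93 = 37.0%; difference 18.5 points.
- Imputing all exits returns about 20% v 40%; difference 20.0 points, a shift of +1.5.

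A simulation (three settings, 1,500 runs each, 20 imputations by arm on baseline only; the SAP specifies 100, with age group and centre) scored 18-21% of placebo and 35-40% of LCM lack-of-efficacy dropouts as responders. The difference moved +0.7 points at 4/4 lack-of-efficacy dropout, about 0 at 8/4, and +2.1 to +2.3 at 4/8. With those dropouts held as non-responders, it stayed within 0.2 points of the primary.

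**5. Other-reason exits as responders, beside all-non-responder.** Completers 20% v 40%, no lack-of-efficacy exits.

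| Exits | Exits as responders | All exits non-responders |
|---|---|---|
| 14/14 | 31.2 v 48.4: 17.2 points | 17.2 v 34.4: 17.2 points |
| 10/18 | 28.0 v 50.8: 22.8 points | 18.0 v 32.8: 14.8 points |
| 18/10 | 34.4 v 46.0: 11.6 points | 16.4 v 36.0: 19.6 points |

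Under no effect (20% in both arms), the responder version rejects 3.6% at 14/14 and 14.9% at 10/18 (exact, corrected chi-square). Each version favours one direction of imbalance; the pair covers both.

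**The case against.** The strongest reply is that these are supportive analyses in a sound set, and much of it stands. Baseline-carried-forward, multiple imputation, per-protocol and 24-hour analyses run beside the arm-mean check. That check bears on the US primary only while early discontinuation is at most 10%. The multiple imputation is a standard missing-at-random method, the effect of its broad scope is small, and disposition by arm and reason (SAP 5.1) will show how many lack-of-efficacy exits there are. None of this repairs the arm-mean standard error or makes the multiple imputation test a single assumption.

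A reader might infer stronger points that the documents do not support.
- *The primary rule is wrong because it omits intolerance and dose-failure exits.* Protocol 6.3 does require those withdrawals and the primary leaves them out, but the planned all-non-responder analysis addresses them directly.
- *Scoring other-reason exits as responders is an error.* It favours whichever arm loses more subjects, so it is no stress test if LCM loses more. But it is one of a planned pair, is the harsher of the two if placebo loses more, and neither document calls it conservative.
- *The planned 14% dropout already triggers the US switch.* Protocol 13.5 treats the 14% as an overall study dropout rate; the trigger in 4.1.1 counts exits after first dose and before the End-of-Maintenance EEG.
- *The documents conflict on who counts as an early discontinuation.* Wording varies, but Protocol 4.1.1 and SAP 8.1.1.1 define the term, and SAP 8.1.2.2 states that lack-of-efficacy exits are included, which answers the broader exclusion in Protocol 13.4.

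**Conclusion.** The arm-mean imputation is wrong as written. Its nominal 5% test rejects about 5-7% at 5/5, 7-9% at 10/10 and 7-10% at 6/10. It would be a mistake to read this as flattering LCM: with equal dropout the excess falls on both sides, and with more LCM exits it falls against LCM. These ranges rest on the assumed seizure models, random dropout and 116 per arm. The Full Analysis Set keeps all treated subjects, so 116 is a working figure; the effect of that choice is small.

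The scope of the EU multiple imputation is a matter of interpretability, worth 0 to about 2 points under the assumed splits. It can be improved at almost no cost. The responder scoring is not an error and needs at most a sentence on how to read it. Nothing here changes the primary analysis or the sample size.

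**What to change.** 1. Delete the arm-mean analysis from Protocol 13.1.1.1 and SAP 8.1.3.1. Cost: one fewer sensitivity analysis.
2. In Protocol 13.1.1.2 and SAP 8.1.3.2-8.1.3.3, state that lack-of-efficacy dropouts remain non-responders in the EU multiple imputation and that only the other early discontinuations are imputed. Cost: one sentence and minor programming, using the classification of reasons that the primary already needs.
3. Optional: say in SAP 8.1.3.2 that the responder scoring favours the arm with more exits and is to be read with the all-non-responder analysis. A worst case (other-reason exits as responders on placebo, non-responders on LCM) may be added as a descriptive bound. It should not be a test to pass: with true 20% v 40% it gives 14.0 points and 59% power at 5/5, 8.0 points and 21% at 10/10, and 3.2 points and 6% at 14/14.

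Make these changes before unblinding.
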